**17.2 Appendix B: Pulmonary Function Test Instructions**

### **Pulmonary Function test (FVC - SITTING)**

[figure not shown]
Forced Vital Capacity (FVC) will be performed in the sitting position.

The patient should be sitting comfortably in a chair. The evaluator explains /demonstrates the procedure to the subject and explains that they will be performing the test at least 3 times. The specific wording of instructions should be followed closely.

- Ask the patient to '*take as big a breath in as possible and then blow out through the mouth as hard and as long as you can*'. The evaluator should verbally encourage the subject to keep going for as long as possible. ATS criteria state a 6 second plateau is required.
- The test should be repeated three times making sure that the patient has recovered between attempts. If at each attempt there is an improvement in the results further tests can be conducted until the subject has achieved his best result.
- The subject can place the mouthpiece in his own mouth unless he is unable to reach his mouth with his hands or flexes his head and shoulders to reach the tube. In this case the evaluator should place the tube into the subject's mouth.
- The tube can be placed in the mouth either before the beginning of inspiration (closed circuit technique) or at the end of inspiration just prior to expiration (open circuit technique) whichever the subject finds most comfortable.
- Whichever technique is used the same method should be used at each evaluation and documented on the worksheets.
- A nose clip should be applied just prior to expiration. If a tight seal cannot be made around the tube then a mask may be used.
- The subject should not be allowed to flex forward during expiration.
- Calibrate the spirometry system on the day of testing

17.3 **Appendix C: Nine Hole Peg Test**

### Nine Hole Peg Test Instructions

Downloaded from [www.rehabmeasures.org](http://www.rehabmeasures.org)  
Test instructions derived from Mathiowetz et al, 1985  
The NHPT is provided courtesy of [name], OTR/L, FAOTA

**Appendix D: Clinical Global Impressions Severity and Improvement**

## CGI-S and CGI-I

The Clinical Global Impression – Severity of Illness (CGI-S) and Clinical Global Impression – Improvement of Illness (CGI-I) are brief, easy to administer, clinician-rated measures (Guy, 1976). The CGI-S asks the clinician to rate the patient's current severity of illness based on the clinician's total clinical experience with the relevant population. The CGI-S is rated on a 7-point scale, with a range of responses from 1 (normal, not at all ill) through 7 (amongst the most extremely ill patients). The CGI-I asks the clinician to rate the patients' total improvement since baseline, whether or not the improvement is judged to be due entirely to the experimental treatment. The CGI-I is rated on a 7-point scale, with a range of responses from 1 (very much improved) to 7 (very much worse). For both the CGI-S and the CGI-I, the clinician is allowed to use all available information at the time of the rating.

The CGI-I has emerged as a convention for bifurcating clinical trial subjects into “responders” and “non-responders”. In this application, the CGI-I can be a useful tool for gaining a general overview of the therapeutic potential of an experimental treatment. One of the relative detriments of both the CGI-S and –I is the lack of the measures' assessment of specific sign or symptoms associated with the disorder under study (Busner et al., 2009). An approach that has been developed to enhance the precision and clinical meaningfulness of CGI ratings is to utilize anchor points that are specific to the signs and symptoms of the disorder under study.

### Clinical Global Impression – Severity of Illness Scale (CGI-S):

“Considering your total clinical experience with myotonic dystrophy patients, how severely ill is this patient at this time?”

- 1- Normal, not at all ill: The patient is indistinguishable from other individuals that do not have myotonic dystrophy (DM). The patient has no overt DM symptoms and no persistent dysfunction in the wake of having been diagnosed with DM.
- 2- Borderline ill: The patient has very occasional DM symptoms that seem modestly excessive in intensity, frequency or duration compared to individuals that have not been diagnosed with DM. These symptoms have only a transient impact on functioning, with no need for any special intervention.
- 3- Mildly ill: The patient has occasional DM symptoms that seem modestly excessive in intensity or duration, or the patient experiences very occasional DM symptoms that are modestly excessive both in intensity and duration as compared to individuals without a DM diagnosis. These symptoms have a limited impact on the patient’s functioning, generally only in one setting, and require that others make some adjustments or accommodations in interacting with this patient.
- 4- Moderately ill: This DM patient is clearly distinguishable from other individuals because of his/her DM symptoms and the impairment that they cause. The patient’s DM symptoms are clearly excessive in frequency, intensity or duration compared to others that have not received a DM diagnosis, and have limited impact on the patient’s functioning in multiple settings or moderate impact in one setting. Caregivers, family members, teachers and co-workers make adjustments when interacting with this patient to avoid exacerbation of his/her symptoms and to deal with them when they occur.
- 5- Markedly ill: This patient’s DM symptoms occur frequently and are noticeable in intensity or duration to even casual observers or occur infrequently but are quite intense or long-lasting. There is moderate impact on the patient’s functioning in multiple settings or extreme impact in one setting. Caregivers, family members, teachers and co-workers utilize interventions that are necessary in order to deal with this patient’s symptoms. Special accommodations related specifically to the patient’s DM symptoms are likely necessary at home, at school or in the workplace.
- 6- Severely ill: The patient’s DM symptoms occur very frequently and are noticeable in intensity or duration to even casual observers or occur infrequently but are severely intense or extremely long-lasting. Often there is marked impairment of normal day-to-day capabilities or skills necessary to function at school or in the workplace. Multiple interventions are required to address the patient’s DM symptoms to minimize consequences.
- 7- Among the most extremely ill patients: The patient’s DM symptoms occur the majority of the time and are very disruptive to functioning in multiple areas. There are very few times, if any, of normal functioning. There are often serious concerns about the patient’s ability to provide adequate care for him/herself as a consequence of the DM symptoms. The patient requires almost constant monitoring by caregivers or others.

Study AMO-02-MD-2-001	Site no.	  	
Subject no.   			
Clinical Global Impression - Severity of Illness Scale (CGI-S)			
Date of assessment	 dd	 mmm	 yyyy
Considering your total clinical experience with myotonic dystrophy patients, how severely ill is this patient at this time?			

1- Normal, not at all ill

2- Borderline ill

3- Mildly ill

4- Moderately ill

5- Markedly ill

6- Severely ill

7- Among the most extremely ill patients

			
Score			
Evaluator name	<hr/>		
Evaluator signature	<hr/>		
Date	 dd	 mmm	 yyyy

## CGI—Improvement – A User’s Guide

1. Very Much Improved designates marked improvement, across settings and/or across multiple problem areas. Although a CGI-I of 1 does not strictly require that the patient qualify for a CGI-S rating better than baseline, usually the CGI-S does also improve. Such improvement must be very substantial and is usually accompanied by considerable patient and/or caregiver enthusiasm. Such patients are usually noticeably improved in the clinic as well.
2. Much Improved may denote moderate improvement in a single symptom area, especially if seen across settings. Likewise, moderate improvements in several areas, even if confined to one setting, may warrant a rating of “Much improved.” Durability of the change should be taken into account. For example, a change reported for the last few hours probably would not warrant such a rating. On the other hand, a change that was clearly in evidence for the last several days or longer probably would warrant a rating of 2. It is not necessary that the patient qualify for a CGI-S rating better than baseline to receive a CGI—I rating of 2, but often (not always) the CGI-S also improves.
3. Minimal Improvement indicates modest improvements, especially if confined to one setting. Trivial changes or changes that are possibly present or require guesswork usually would be scored as 4 (the level below this one).
4. No Change indicates, by definition, the absence of change in behavior or clinical presentation from baseline to subsequent assessments. Chance fluctuations and equivocal improvements or declines should be included here.
5. Minimally Worse indicates some worsening in symptoms that are mild to moderate or may be confined to one setting.
6. Much Worse designates moderate to moderately severe worsening. This may include moderate levels of worsening in a single symptom area when observed across settings. Moderately severe changes that are confined to one setting may warrant a rating of “Much Worse.”
7. Very Much Worse designates significant worsening, across settings and/or across multiple symptoms.

**N.B.** The CGI-I is a rating of *change*; normalization is not necessary for a rating of 1, although if the clinical presentation is unequivocally improved and is evident across settings, it suggests an Improvement score of 1. A CGI-I of 2 is appropriate for definite, unequivocal improvement of a magnitude that makes the clinician confident that the treatment is helping. An improvement score of 3 (or 5) is appropriate if variations in ratings and other criteria appear to represent more than random chance or rating error, but are not definite and unequivocal. A score of 4 is appropriate for slight variation in either direction of a magnitude that is likely due to chance, natural history, external events, or rating error.

[figure not shown]
[figure not shown]
Study AMO-02-MD-2-001	Site no. 	
Subject no. 		
Clinical Global Impression - Global Improvement Scale (CGI-I)		
Date of assessment	 dd  mmm  yyyy	
Compared to the baseline assessment* in this study, if you consider the signs and symptoms associated with this patient's myotonic dystrophy, how much has he/she changed? Rate his/her total improvement whether or not, in your judgement, it is due entirely to the study drug.		

1- Very much improved 2- Much improved 3- Minimally improved 4- No change 5- Minimally worse 6- Much Worse 7- Very much worse
 

		
Score		
Evaluator name	<hr/>	
Evaluator signature	<hr/>	
Date	 dd  mmm  yyyy	

**17.5 Appendix E: Subject and Caregiver Top 3 Concerns**

Study AMO-02-MD-2-001	Site no.  /  / 	
Subject no.  /  / 		
Caregiver Top Three Concerns Baseline		
Date of assessment  dd /  mmm /  yyyy		
Please rate the three causes for concern associated with your relative and their myotonic dystrophy that you would most like to see change during treatment. You can select any sign or symptom.		
Your Concerns		
Concern number 1		
The sign or symptom causing concern is:		
How severe is the sign or symptom? Place a vertical mark on the line below to indicate how bad you think the sign or symptom has been in the past week, including today.		
 Completely Absent —————  Very Severe		
Concern number 2		
The sign or symptom causing concern is:		
How severe is the sign or symptom? Place a vertical mark on the line below to indicate how bad you think the sign or symptom has been in the past week, including today.		
 Completely Absent —————  Very Severe		
Concern number 3		
The sign or symptom causing concern is:		
How severe is the sign or symptom? Place a vertical mark on the line below to indicate how bad you think the sign or symptom has been in the past week, including today.		
 Completely Absent —————  Very Severe		

Study AMO-02-MD-2-001	Site no.   	
Subject no.   		
Subject Top Three Concerns Baseline		
Date of assessment  dd  mmm  yyyy		
Please rate the three causes for concern associated with your myotonic dystrophy that you would most like to see change during treatment. You can select any sign or symptom.		
Your Concerns		
Concern number 1		
The sign or symptom causing concern is:		
How severe is the sign or symptom? Place a vertical mark on the line below to indicate how bad you think the sign or symptom has been in the past week, including today.		
 Completely Absent  Very Severe		
Concern number 2		
The sign or symptom causing concern is:		
How severe is the sign or symptom? Place a vertical mark on the line below to indicate how bad you think the sign or symptom has been in the past week, including today.		
 Completely Absent  Very Severe		
Concern number 3		
The sign or symptom causing concern is:		
How severe is the sign or symptom? Place a vertical mark on the line below to indicate how bad you think the sign or symptom has been in the past week, including today.		
 Completely Absent  Very Severe		

Study AMO-02-MD-2-001	Site no.  /  / 	
Subject no.  /  / 		
Subject Top Three Concerns Follow-Up		
Date of assessment  dd /  mmm /  yyyy		
At baseline, you rated the three causes for concern, related to your myotonic dystrophy that you most liked to see change during treatment. You selected the following signs or symptoms.		
Your Concerns		
Concern number 1		
The sign or symptom causing concern was:		
How severe is the sign or symptom? Place a vertical mark on the line below to indicate how bad you think the sign or symptom has been over the past week, including today.		
		
Concern number 2		
The sign or symptom causing concern was:		
How severe is the sign or symptom? Place a vertical mark on the line below to indicate how bad you think the sign or symptom has been over the past week, including today.		
		
Concern number 3		
The sign or symptom causing concern was:		
How severe is the sign or symptom? Place a vertical mark on the line below to indicate how bad you think the sign or symptom has been over the past week, including today.		
		

17.6 **Appendix F: Clinician-completed Domain Specific Causes for Concern:  
Myotonic Dystrophy (VAS)**

Study AMO-02-MD-2-001	Site no. 	
	Subject no. 	

### Clinician Domain-Specific Causes for Concern: Myotonic Dystrophy - Page 1 of 5

Date of assessment

dd       mmm       yyyy

Please rate the causes for concern you would most like to see change during treatment in the categories below. Your choice should be associated with the subject's myotonic dystrophy. You can select any sign or symptom fitting the category. You should choose one specific concern for each category. If there is no concern in any symptom area, write "None" and mark at the end "Not at all severe". When rating the severity of the item, please focus on the past week.

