### **9.3 Allocation to Treatment**

This study is single-blind, where the Sponsor/delegate and the Investigator site will know what treatment the subjects is receiving at each point during the study, but the subject and caregiver will be blinded to know if they are receiving active or placebo. Subjects will be allocated into Cohort 1 (1000mg) or 2 (400mg) in sequence.

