### **10.2.9 Clinician completed Domain Specific Causes for Concern VAS: Myotonic Dystrophy**

The Clinician-completed Domain Specific Concerns is a Visual Analogue Scale (VAS) completed by the clinician that scores the severity of concerns in the following domains that are clinically relevant in myotonic dystrophy:

- Limitations with mobility or walking
- Problems with hands or arms
- Inability to do activities
- Fatigue
- Pain
- Gastrointestinal issues
- Problems with vision
- Communication difficulties
- Impaired sleep or daytime sleepiness
- Emotional issues
- Difficulty thinking
- Decreased satisfaction in social situations
- Decreased performance in social situations
- Myotonia
- Breathing difficulties
- Choking or swallowing issues
- Hearing difficulties

This list of domains is derived from the 17 subscales of the Myotonic Dystrophy Health Index (MDHI) (Heatwole *et al.*, 2014). The severity of the clinician's concern in each domain is scored by using a 10-cm visual analogue scale (VAS), with anchors of "not at all severe" at the left end and "very severe" at the right end. The clinician is asked to make a vertical line indicating his/her level of concern in each domain, using a time frame of the past week for reference. A score for each domain is determined by measuring the number of centimetres on the 10-cm VAS line from the anchor point on the left side of the line. A total VAS score for each subject is calculated as the sum of the scores for the 17 domains and is reported as both an absolute number and a percentage of the total possible line length (e.g. 170 cm).

The Clinician-completed Domain Specific Causes for Concern-VAS: Myotonic Dystrophy will be administered according the schedule of assessments.

A copy of the Clinician Domain Specific Causes for Concern VAS: Myotonic Dystrophy is included in Appendix F.

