#### 1. Limitations with mobility or walking

Examples might include ankle turning, not being able to walk to the front door fast enough when there is a caller, needing help to move around the home. You can choose a different example.

The sign or symptom causing concern is:

How severe is the sign or symptom? Place a vertical mark on the line below to indicate how bad you think the sign or symptom has been over the past week, including today.

[figure not shown]

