#### 15. Breathing difficulties

Examples breathlessness whilst walking, or sleep apnea. You can choose a different example.

The sign or symptom causing concern is:

How severe is the sign or symptom? Place a vertical mark on the line below to indicate how bad you think the sign or symptom has been over the past week, including today.

Study AMO-02-MD-2-001	Site no. 	
	Subject no. 	

### Clinician Domain-Specific Causes for Concern: Myotonic Dystrophy - Page 5 of 5

Please rate the causes for concern associated with the subject's myotonic dystrophy that you would most like to see change during treatment in the categories below. You can select any sign or symptom fitting the category.

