5.1.2.2 Clinician-completed Domain Specific Causes for Concern VAS: Myotonic Dystrophy

A MMRM model will be fitted to the change from baseline to weeks [redacted] and [redacted] in the total clinician-completed domain specific causes for concern VAS score. The model will be fitted and results presented as described in section 5.1.1.1.

The observed total clinician-completed domain specific causes for concern VAS score and domain specific VAS scores and corresponding change from baseline will be summarised over time. In addition, the above scores at [redacted] and [redacted] and the change from [redacted] to [redacted] will be summarised. The observed total clinician-completed domain specific causes for concern VAS score and domain specific VAS scores will also be presented over time ([redacted] and [redacted]) using by subject line plots by dose group. In addition, line plots will present the adjusted LS mean changes from baseline and SEs over time, as estimated by the MMRM model, by dose group for

the total clinician-completed domain specific causes for concern VAS score. Raw mean changes from [redacted] to [redacted] will be presented on the same plot.

The relationship between the change from baseline to week [redacted] in the total clinician-completed domain specific causes for concern VAS score and the change from baseline to week [redacted] in total lean muscle mass will be evaluated by plotting the change from baseline to week [redacted] in the total clinician-completed domain specific causes for concern VAS score against the change from baseline to week [redacted] in total lean muscle mass.

The clinician-completed domain specific causes for concern VAS data will be listed.

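### The clinician Domain Specific VAS scores a symptom the clinician picks in each domain, and nothing keeps that symptom for later visits, so change from baseline can mix symptom choice with severity

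*Protocol*

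**What the plan says.** Protocol 10.2.9 says the instrument "is a Visual Analogue Scale (VAS) completed by the clinician that scores the severity of concerns in the following domains". It then lists 17 domains, each marked on a 10 cm line, and defines the total as the sum of the 17 marks, out of 170 cm.

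The form in Appendix F works differently. Its instruction reads "You can select any sign or symptom fitting the category. You should choose one specific concern for each category". Each domain has a blank line on which the clinician writes a symptom. The VAS question then asks how severe that symptom was over the past week. The printed examples do not bind the clinician: "You can choose a different example". Where there is no concern, the clinician writes 'None' and marks the lowest end of the line.

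The Top 3 Concerns VAS is handled otherwise. Protocol 10.2.8 has the three concerns chosen at baseline and the same three rated again. Appendix E includes a subject follow-up form that begins "At baseline, you rated the three causes for concern, related to your myotonic dystrophy that you most liked to see change during treatment" and restates the symptoms chosen then.

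Protocol 9.3 says "the Investigator site will know what treatment the subjects is receiving at each point during the study". SAP 5.1.2.2 fits an MMRM to the change from baseline in the total, and "domain specific VAS scores and corresponding change from baseline will be summarised over time". SAP 3.1.1 and Appendix 2 add an ad hoc Cohort 1 analysis of the total, with p-values and Cohen's d. SAP 3.1.5 adds plots of percentage change.

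**The concern.** A change score is interpretable when the same thing is rated both times. Here the clinician could name fastening buttons under hands and arms at baseline and typing at end of treatment. The difference between the two marks would then reflect two symptoms as well as any change in the patient. A milder symptom at the later visit would look like benefit. Replacing an improved symptom with a worse one would hide benefit.

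The person who names the symptom also knows whether the subject is on placebo or tideglusib. Protocol 10.2.7 asks for the same evaluator at each visit for the CGI. Protocol 10.2.9 has no such provision, so two clinicians could pick different symptoms for the same subject. What is at stake is the reading of one secondary efficacy endpoint that is given model-based p-values in cohorts of eight.

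**Working it through.** **Does the plan fix the symptom anywhere?**

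| | Clinician Domain VAS | Top 3 Concerns VAS |
|---|---|---|
| What the protocol text says is rated | Concern in a domain (10.2.9) | Three concerns chosen at baseline (10.2.8) |
| What the form rates | One named symptom per domain (Appendix F) | Three named symptoms (Appendix E) |
| Rule to re-rate the same symptom | None in 10.2.9, Appendix F or SAP 5.1.2.2 | Stated in 10.2.8 |
| Follow-up form restating the symptom | None | Yes, in Appendix E |

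The absence is unlikely to come from missing pages. The contents list puts Appendix F at page 106 and Appendix G at page 112, so Appendix F has 112 − 106 = 6 pages. The form numbers itself as five pages, the last headed "Clinician Domain-Specific Causes for Concern: Myotonic Dystrophy - Page 5 of 5". One title page plus five form pages accounts for all six. The form carries no baseline or follow-up label. Its instruction, to rate what the clinician would most like to see change during treatment, suits a first rating.

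**The plan's own figure.** 17 domains × 10 cm = 170 cm, as stated in 10.2.9.

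**Possible size.** The documents give no rate of symptom switching and no SD, so these values are assumed: a switch changes the mark by d = 3 cm, in m = 2, 4 or 6 domains, with no change in the patient.

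- All switches in one direction: shift in the subject's total = m × d.
- Each switch independently +3 or −3 cm with equal chance: mean shift = 0, SD = d × √m.
- Mean of eight such subjects (eight per dose group, SAP 2.4): SD = d × √m / √8.

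| m | One direction, m × 3 | Share of 170 cm | Random, 3 × √m | Random, mean of 8 |
|---|---|---|---|---|
| 2 | 6 cm | 3.5% | 4.2 cm | 1.5 cm |
| 4 | 12 cm | 7.1% | 6.0 cm | 2.1 cm |
| 6 | 18 cm | 10.6% | 7.3 cm | 2.6 cm |

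The one-direction column is an upper limit for the assumed d and m. The cohort mean moves by that much only if all eight subjects are affected alike. If one subject of eight is affected, it moves by 6/8 = 0.75, 12/8 = 1.5 or 18/8 = 2.25 cm. A single domain can move the total by at most 10 cm (10/170 = 5.9%).

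**The case against.** Section 10.2.9 describes domain-level concern. If that governs, hands and arms at baseline against hands and arms at end of treatment is one construct even when the leading symptom differs, and a switch matters much less. This stands as far as it goes: the documented fault is first a mismatch between 10.2.9 and Appendix F. It does not remove the problem, because sites complete the form, and the form asks about the named symptom.

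A carry-forward rule could sit in the eCRF or in site training. Neither document says so, and neither shows that symptoms were in fact re-chosen.

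Three stronger readings are tempting, and the documents do not support them.

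- A reader might infer that switching favours tideglusib because the rater is unblinded. It can run either way. Choosing a milder symptom would also go against the form's instruction to rate what the clinician most wants to see change. An unblinded rater can shift the mark for an unchanged symptom just as easily, so carrying symptoms forward would not remove that bias.
- A reader might count a move from a named symptom to 'None' as an artefact. The form reserves 'None' for no concern, so such a move is a genuine resolution and should score near zero on any version.
- A reader might take 6 to 18 cm as the expected distortion. It requires every switch to go the same way. With random directions the effect is added noise.

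The consequence is also limited: this is one of many secondary endpoints in a 16-subject safety study with no power calculation.

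**Conclusion.** The point holds in a limited form. The protocol text and the form disagree about what is scored. Nothing in either document keeps the symptom named at the first rating. The change scores in SAP 5.1.2.2 and the Cohort 1 contrasts can therefore mix symptom choice with change in severity, and the plan has no check that would show whether they do. That switching occurs, how often, and which way it pushes cannot be settled from the documents. The sizes in the table rest wholly on the assumed 3 cm and 2, 4 or 6 domains. This should be corrected because it affects how the p-values for this endpoint can be read. It does not touch the primary safety objective.

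**What to change.** 1. Reconcile Protocol 10.2.9 with Appendix F: state whether the domain or the named symptom is scored.

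2. In SAP 5.1.2.2, for both cohorts, list the named symptom by visit and flag each domain where it changed to a different symptom. Do not flag a move to 'None'. State in advance how a domain first marked 'None' and later given a symptom is handled; dropping only those domains would tilt the result towards improvement.

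3. Add a sensitivity analysis of the total on domains with the same symptom at both visits, as a mean per domain or a percentage of available line length. With 2, 4 or 6 domains switched, 15, 13 or 11 remain (150, 130 or 110 cm), so raw sums would not be comparable between subjects. Read the MMRM and Cohort 1 p-values alongside it.

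4. If ratings are still to come, pre-print the first-rating symptom on a follow-up form, as Appendix E does. Report new or worsened concerns as a separate score. Re-rating only the concerns chosen at the start, with new ones left unreported, would favour apparent improvement.

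5. SAP 3.1 shows that Cohort 1 outputs have already been produced, and cohorts are filled in sequence. A new form would then reach Cohort 2 only. Keep the current scoring as the main by-dose comparison, or state that form version is confounded with dose.

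The cost is a little extra analysis and, where ratings remain, a revised form. No extra visit or procedure is needed, because the form already has the clinician write the symptom down. The sensitivity total rests on fewer domains, selected after baseline, so it is supportive only.
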